5.7 Duration of Follow-up

Follow-up frequency is calculated from date of surgery. After surgery, patients will be followed every 12 weeks for 2 years and every 24 weeks for 1 additional year. Frequency and duration of follow-up after the end of treatment depends on when treatment is discontinued. Patients will be followed for 3 years from date of surgery regardless of when treatment is discontinued unless treatment is discontinued due to disease recurrence, in which case the patient will be considered off study after the 90-day follow-up for adverse events is completed. Patients removed from study for unacceptable adverse events will be followed until resolution or stabilization of the adverse event.

5.8 Lost to Follow-Up

A patient will be considered lost to follow-up if he or she fails to return for 2 scheduled visits and is unable to be contacted by the study team.

The following actions must be taken if the patient fails to return to clinic for a required study visit:

- The study team will attempt to contact the patient and reschedule the missed visit within 2 weeks and counsel the patient on the importance of maintaining the assigned visit schedule and ascertain if the patient wishes to and/or should continue in the study.
- Before a patient is deemed lost to follow-up, the investigator or designee will make every effort to regain contact with the patient (where possible, 3 telephone calls and, if necessary, a certified letter to the patient's last known mailing address). These contact attempts should be documented in the patient's medical record or study file.
- Should the patient continue to be unreachable, he or she will be considered to have withdrawn from the study with a primary reason of lost to follow-up.

6.0 DOSE DELAYS/DOSE MODIFICATIONS

Other holds and modifications beyond what is described below may be made at the discretion of the PI.

6.1 Dose Modifications

There will be no dose modifications, including dose reductions, for atezolizumab or tiragolumab in this study.

6.2 Treatment Interruptions

Study treatment may be temporarily suspended as appropriate for management of toxicity. On the basis of the available characterization of mechanism of action, tiragolumab may cause adverse events similar to but independent of atezolizumab, may exacerbate the frequency or severity of atezolizumab related adverse events, or may have non overlapping toxicities with atezolizumab. Because these scenarios may not be distinguished from one another in the clinical setting, immune mediated adverse events should generally be attributed to both study drugs, and dose interruptions or treatment discontinuation in response to immune mediated adverse events should be applied to both atezolizumab and tiragolumab.

In the adjuvant setting, atezolizumab and tiragolumab may be held for a maximum of 12 weeks. If tiragolumab is interrupted for > 12 weeks for any reason, the patient must permanently discontinue tiragolumab treatment, but may continue atezolizumab if there is no contraindication and after discussion with the PI to determine whether the toxicity is considered related to tiragolumab and/or to the combination. An exception can be made if in the judgment of the investigator, the patient is likely to derive clinical benefit from resuming tiragolumab after a hold of > 12 weeks. In this case, tiragolumab may be restarted with the approval of the PI. If atezolizumab is interrupted for > 12 weeks, the patient must permanently discontinue atezolizumab. However, if, in the judgment of the investigator, the patient is likely to derive clinical benefit from atezolizumab after a hold of > 12 weeks, atezolizumab may be restarted with the approval of the PI. Continued dosing of patients with single agent atezolizumab will require that all other study eligibility criteria continue to be met. Continued administration of single agent tiragolumab after permanent discontinuation of atezolizumab is not permitted.

If a patient must be tapered off steroids used to treat adverse events, atezolizumab and/or tiragolumab may be withheld for additional time beyond > 12 weeks from the last dose until steroids are discontinued, or until steroids are reduced to prednisone dose (or dose equivalent) ≤ 10 mg/day. The acceptable length of interruption will depend on an agreement with the PI.

Dose interruptions for reason(s) other than toxicity may be allowed with PI approval.

6.2.1 Study treatment discontinuation criteria specific to tiragolumab or atezolizumab-related AEs

- Any Grade ≥ 2 treatment-related uveitis, eye pain, or blurred vision that does not respond to topical therapy and does not improve to Grade 1 severity within 8 weeks or requires systemic treatment.

- Any Grade ≥ 2 treatment-related pneumonitis or interstitial lung disease that does not resolve following dose delay and systemic steroids.
- For Grade ≥ 3 adrenal insufficiency or Grade ≥ 4 hypophysitis, treatment needs to be discontinued regardless of control with hormone replacement (Note: Hospitalization for diagnostic workup of adrenal insufficiency without severe symptoms should not require discontinuation).
- Any Grade ≥ 3 non-skin, treatment-related AE lasting > 7 days or recurs, with the following exceptions for uveitis, pneumonitis, bronchospasm, diarrhea, colitis, neurologic toxicity, hypersensitivity reactions, infusion reactions, endocrinopathies, and laboratory abnormalities:
 - Grade 3 treatment-related uveitis, pneumonitis, bronchospasm, diarrhea, colitis, neurologic toxicity, hypersensitivity reaction, or infusion reaction of any duration requires discontinuation.
 - Grade 3 treatment-related endocrinopathies (excluding adrenal insufficiency and hypophysitis) adequately controlled with only physiologic hormone replacement do not require discontinuation.
 - Grade 3 treatment-related laboratory abnormalities do not require treatment discontinuation except:
 - Grade 3 treatment-related thrombocytopenia > 7 days or associated with clinically significant bleeding requires discontinuation.
- In most cases of Grade 3 AST or ALT elevation, study treatment will be permanently discontinued. If the Investigator determines a possible favorable benefit/risk ratio that warrants continuation of study treatment, a discussion between the Investigator and the Medical Monitor/designee must occur.
- Any treatment-related liver function test abnormality that meets the following criteria require discontinuation:
 - AST or ALT $> 5 \times$ ULN to $8 \times$ ULN for > 2 weeks
 - AST or ALT $> 8 \times$ ULN
 - Total bilirubin $> 5 \times$ ULN
 - Concurrent AST or ALT $> 3 \times$ ULN and total bilirubin $> 2 \times$ ULN
- Grade 3 or 4 infusion reaction of any duration
- Any Grade 4 treatment -related AE or laboratory abnormality, except for the following events, which do not require discontinuation:
 - Grade 4 neutropenia ≤ 7 days.
 - Grade 4 lymphopenia or leukopenia ≤ 14 days in duration.
 - Isolated Grade 4 amylase or lipase abnormalities that are not associated with symptoms or clinical manifestations of pancreatitis and decrease to Grade < 4 or return to baseline within 7 days.
 - Isolated Grade 4 electrolyte imbalances/abnormalities that are not associated with clinical sequelae and are corrected with supplementation/appropriate management within 72 hours of their onset.
 - Grade 4 treatment -related endocrinopathy AEs (except adrenal insufficiency or hypophysitis), such as hyper- or hypothyroidism, or glucose intolerance, which resolve or are adequately controlled with physiologic hormone replacement (corticosteroids at ≤ 10 mg of prednisone or equivalent per day, thyroid hormones) or glucose-controlling agents,

respectively, may not require discontinuation after discussion with and approval from the Medical Monitor.

- Any AE, laboratory abnormality, or intercurrent illness that, in the judgment of the Investigator, presents a substantial clinical risk to the patient with continued treatment.
- Disease recurrence (local, regional, or distant), including new primary melanoma (except MMIS Stage 0) Note: Non-melanoma skin cancer does not require treatment discontinuation. In the absence of intolerable toxicity, patients with diagnosed MMIS Stage 0 melanoma will be eligible to continue study treatment using the same dose and schedule for their original melanoma of up to approximately 1 year of study treatment starting from first dose, at the discretion of the Investigator.

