| Diarrhea or colitis, Grade 3 | 
 ● Withhold atezolizumab and tiragolumab for up to 12 weeks after event onset.^a ● Refer patient to GI specialist for evaluation and confirmatory biopsy. ● Initiate treatment with corticosteroids equivalent to 1–2 mg/kg/day IV methylprednisolone and convert to 1–2 mg/kg/day oral prednisone or equivalent upon improvement. If event does not improve within 48 hours after initiating corticosteroids, consider adding an immunosuppressive agent. ● If event resolves to Grade 1 or better, resume atezolizumab and tiragolumab.^b ● If event does not resolve to Grade 1 or better while withholding atezolizumab and tiragolumab, permanently discontinue atezolizumab and tiragolumab and contact Medical Monitor.^c |
| Diarrhea or colitis, Grade 4 | 
 ● Permanently discontinue atezolizumab and tiragolumab and contact Medical Monitor.^c ● Refer patient to GI specialist for evaluation and confirmatory biopsy. ● Initiate treatment with corticosteroids equivalent to 1–2 mg/kg/day IV methylprednisolone and convert to 1–2 mg/kg/day oral prednisone or equivalent upon improvement. ● If event does not improve within 48 hours after initiating corticosteroids, consider adding an immunosuppressive agent. ● If event resolves to Grade 1 or better, taper corticosteroids over \geq 1 month. |

| Event | Management |
|-------|------------|
|-------|------------|

GI = gastrointestinal.

- ^a Atezolizumab and tiragolumab may be withheld for a longer period of time (i.e., > 12 weeks after event onset) to allow for corticosteroids (if initiated) to be reduced to the equivalent of ≤ 10 mg/day oral prednisone. The acceptable length of the extended period of time must be based on the investigator's benefit-risk assessment and in alignment with the protocol requirements for the duration of treatment and documented by the investigator.
- ^b If corticosteroids have been initiated, they must be tapered over ≥ 1 month to the equivalent of ≤ 10 mg/day oral prednisone before atezolizumab and tiragolumab can be resumed.
- ^c Resumption of atezolizumab and tiragolumab may be considered in patients who are deriving benefit and have fully recovered from the immune-mediated event. Patients can be re-challenged with atezolizumab and tiragolumab only after approval has been documented by the investigator.

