| Hyperthyroidism, Grade 1 | 
TSH \geq 0.1 mU/L and $<$ 0.5 mU/L:
 
 ● Continue atezolizumab and tiragolumab. ● Monitor TSH every 4 weeks. ● Consider patient referral to endocrinologist 
TSH $<$ 0.1 mU/L:
 
 ● Follow guidelines for Grade 2 hyperthyroidism. ● Consider patient referral to endocrinologist |
| Hyperthyroidism, Grade 2 | 
 ● Consider atezolizumab and tiragolumab. ● Initiate treatment with anti-thyroid drug such as methimazole or carbimazole as needed. ● Consider patient referral to endocrinologist. ● Resume atezolizumab and tiragolumab when symptoms are controlled and thyroid function is improving. |
| Grade 3 and 4 hyperthyroidism | 
 ● Withhold atezolizumab. ● Initiate treatment with anti-thyroid drug such as methimazole or carbimazole as needed. ● Refer to an endocrinologist. ● Resume atezolizumab and tiragolumab when symptoms are controlled, and thyroid function is improving. ● Permanently discontinue atezolizumab.^c |
| Adrenal insufficiency, Grade 2–4 | 
 ● Withhold atezolizumab and tiragolumab for up to 12 weeks after event onset.^a ● Refer patient to endocrinologist. ● Perform appropriate imaging. ● Initiate treatment with corticosteroids equivalent to 1–2 mg/kg/day IV methylprednisolone and convert to 1–2 mg/kg/day oral prednisone or equivalent upon improvement. ● If event resolves to Grade 1 or better and patient is stable on replacement therapy, resume atezolizumab and tiragolumab.^b ● If event does not resolve to Grade 1 or better or patient is not stable on replacement therapy while withholding atezolizumab and tiragolumab, permanently discontinue atezolizumab and tiragolumab and contact PI.^c |
| Hypophysitis (panhypopituitarism), Grade 2 or 3 | 
 ● Withhold atezolizumab and tiragolumab for up to 12 weeks after event onset.^a ● Refer patient to endocrinologist. ● Perform brain MRI (pituitary protocol). ● Initiate treatment with corticosteroids equivalent to 1–2 mg/kg/day IV methylprednisolone and convert to 1–2 mg/kg/day oral prednisone or equivalent upon improvement. ● Initiate hormone replacement if clinically indicated. ● If event resolves to Grade 1 or better, resume atezolizumab and tiragolumab.^b |

| Event | Management |
|--|---|

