6.3.10 Pancreatic Events

The differential diagnosis of acute abdominal pain should include pancreatitis. Appropriate workup should include an evaluation for ductal obstruction, as well as

serum amylase and lipase tests. Management guidelines for pancreatic events, including pancreatitis, are provided in the table below.

Management Guidelines for Pancreatic Events, Including Pancreatitis

| Event | Management |
|---|---|
| Amylase and/or lipase elevation, Grade 2 | 
Amylase and/or lipase > 1.5-2.0 · ULN:
 
 ● Continue atezolizumab and tiragolumab. ● Monitor amylase and lipase weekly. ● For prolonged elevation (e.g., > 3 weeks), consider treatment with corticosteroids equivalent to 10 mg/day oral prednisone. 
Asymptomatic with amylase and/or lipase > 2.0-5.0 · ULN:
 
 ● Treat as a Grade 3 event. |
| Amylase and/or lipase elevation, Grade 3 or 4 | 
 ● Withhold atezolizumab and tiragolumab for up to 12 weeks after event onset.^a ● Refer patient to GI specialist. ● Monitor amylase and lipase every other day. ● If no improvement, consider treatment with corticosteroids equivalent to 1-2 mg/kg/day oral prednisone. ● If event resolves to Grade 1 or better, resume atezolizumab and tiragolumab.^b ● If event does not resolve to Grade 1 or better while withholding atezolizumab and tiragolumab, permanently discontinue atezolizumab and tiragolumab and contact PI.^c ● For recurrent events, permanently discontinue atezolizumab and tiragolumab and contact PI.^c |
| Immune-mediated pancreatitis, Grade 2 or 3 | 
 ● Withhold atezolizumab and tiragolumab for up to 12 weeks after event onset.^a ● Refer patient to GI specialist. ● Initiate treatment with corticosteroids equivalent to 1-2 mg/kg/day IV methylprednisolone and convert to 1-2 mg/kg/day oral prednisone or equivalent upon improvement. ● If event resolves to Grade 1 or better, resume atezolizumab and tiragolumab.^b ● If event does not resolve to Grade 1 or better while withholding atezolizumab and tiragolumab, permanently discontinue atezolizumab and tiragolumab and contact PI.^c ● For recurrent events, permanently discontinue atezolizumab and tiragolumab and contact PI.^c |

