7.1.3.1 Adverse Events of Special Interest

Adverse events of special interest are required to be reported by the investigator to Genentech immediately (i.e., no more than 24 hours after learning of the event; see Section 5.4.2 for reporting instructions). Adverse events of special interest for this study are as follows:

- Cases of potential drug-induced liver injury that include an elevated ALT or AST in combination with either an elevated bilirubin or clinical jaundice, as defined by Hy's Law (see Section 5.3.5.7)
- Suspected transmission of an infectious agent by the study treatment, as defined as: Any organism, virus, or infectious particle (e.g., prion protein transmitting transmissible spongiform encephalopathy), pathogenic or non-pathogenic, is considered an infectious agent. A transmission of an infectious agent may be suspected from clinical symptoms or laboratory findings that indicate an infection in a patient exposed to a medicinal product. This term applies only when a contamination of study treatment is suspected.

- Pneumonitis
- Colitis
- Endocrinopathies: diabetes mellitus, pancreatitis, adrenal insufficiency, hyperthyroidism, and hypophysitis
- Hepatitis, including AST or ALT > 10 x ULN
- Systemic lupus erythematosus
- Neurological disorders: Guillain Barré syndrome, myasthenic syndrome or myasthenia gravis, and meningoencephalitis, facial paresis, myelitis
- Events suggestive of hypersensitivity, infusion-related reactions, cytokine release syndrome, and hemophagocytic lymphohistiocytosis,
- Pericardial disorders
- Nephritis
- Ocular toxicities (e.g., uveitis, retinitis, optic neuritis)
- Myositis
- Myopathies, including rhabdomyolysis
- Grade ≥ 2 cardiac disorders
- Vasculitis
- Autoimmune hemolytic anemia
- Severe cutaneous reactions (e.g., Stevens-Johnson syndrome, dermatitis bullous, toxic epidermal necrolysis)

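### Sections 6.2.1 and 6.3 give opposite restart instructions for treatment-related Grade 3 diarrhea/colitis and for Grade 3–4 adrenal insufficiency, and nothing says which section governs

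*Combined protocol and SAP*

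**What the plan says.** Section 6.2.1 lists when treatment must stop for drug-related events. These rules matter here:

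- For a named group of events, "Grade 3 treatment-related uveitis, pneumonitis, bronchospasm, diarrhea, colitis, neurologic toxicity, hypersensitivity reaction, or infusion reaction of any duration requires discontinuation".
- For adrenal insufficiency of Grade 3 or worse, "treatment needs to be discontinued regardless of control with hormone replacement". A note spares patients who are hospitalised only for a diagnostic work-up without severe symptoms. The later exception for Grade 4 endocrinopathies leaves adrenal insufficiency and hypophysitis out.
- Treatment also stops for a Grade 3 or worse "non-skin, treatment-related AE lasting > 7 days or recurs", with listed exceptions. One exception covers Grade 3 endocrinopathies (again not adrenal insufficiency or hypophysitis) that are "adequately controlled with only physiologic hormone replacement do not require discontinuation".
- Grade 4 laboratory abnormalities stop treatment. An isolated, asymptomatic amylase or lipase rise is spared only if it drops below Grade 4 or reaches baseline within 7 days.

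Section 6.3 gives management tables by organ system. The Grade 3 row of 6.3.3 (diarrhea or colitis) holds both drugs for up to 12 weeks, starts steroids, and then says "If event resolves to Grade 1 or better, resume atezolizumab and tiragolumab". The adrenal row of 6.3.4 covers Grades 2 to 4 together and says "If event resolves to Grade 1 or better and patient is stable on replacement therapy, resume atezolizumab and tiragolumab". A resume line also appears for Grade 3 myositis (6.3.15), for the row headed "Immune-mediated pancreatitis, Grade 2 or 3" and the Grade 3 or 4 amylase/lipase row (both 6.3.10), and for Grade 2 or 3 hypophysitis (6.3.4). Footnote b requires any steroid course to be tapered over at least 1 month before restarting.

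**The concern.** For the same patient, one section orders a permanent stop and the other orders a restart, so a site cannot follow both. If it follows the 6.3 row, it re-doses someone whom 6.2.1 takes off treatment. If it follows 6.2.1, it withholds doses that 6.3 tells it to give.

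The trial is multicenter, so sites may resolve the contradiction differently. The patients have resected stage II disease, and Section 1.1 justifies biomarker selection partly by the wish to spare patients needless toxicity. Two reported quantities also depend on the rule followed. The safety endpoint in the Section 2 table includes discontinuations due to treatment-related AEs, and Section 5.3 replaces Stage 1 patients who discontinue before C3D1.

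**Working it through.** No formula tests the contradiction itself, so the rules are set side by side. Each row assumes that the event recovers to Grade 1 or better during the hold.

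| Event (treatment-related) | 6.2.1 | 6.3 | Conflict |
|---|---|---|---|
| Grade 3 diarrhea/colitis | stop, any duration | 6.3.3: resume | unconditional |
| Grade 3–4 adrenal insufficiency | stop, whatever the hormone control | 6.3.4: resume if stable on replacement | unconditional, apart from the work-up note |
| Grade 3 myositis | stop if over 7 days | 6.3.15: resume | only if over 7 days |
| Grade 3 pancreatitis | stop if over 7 days | 6.3.10: resume | only if over 7 days |
| Grade 4 amylase/lipase | stop unless below Grade 4 or at baseline within 7 days | 6.3.10: resume | only if that limit is missed |
| Grade 3 hypophysitis | outside the endocrinopathy exception, so arguably the 7-day rule | 6.3.4: resume | arguable, only if over 7 days |

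On recurrence, the myositis and pancreatitis rows also discontinue, so they agree with 6.2.1 there.

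**Can pancreatitis escape through the endocrinopathy exception?** Section 7.1.3.1 does list "Endocrinopathies: diabetes mellitus, pancreatitis, adrenal insufficiency, hyperthyroidism, and hypophysitis". But the exception requires control by physiologic hormone replacement alone, and 6.3.10 treats pancreatitis with 1–2 mg/kg/day methylprednisolone. It does not fit.

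**Does any text rank the sections?** Section 6.0 gives the PI discretion over holds and modifications other than those described, which sets no order. Section 5.6 has its own stopping list and does not cite 6.2.1. In the disputed rows, footnote c (re-challenge) is attached to the permanent-discontinuation lines, so it does not explain the resume lines.

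**Doses at stake.** Treatment is up to 13 cycles (5.6). For an event after dose k, 6.2.1 allows 0 further doses and 6.3 allows at most 13 − k:

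- k = 2: 13 − 2 = 11
- k = 6: 13 − 6 = 7
- k = 12: 13 − 12 = 1

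These are ceilings. A 12-week hold spans up to 12/4 = 3 scheduled doses, and the plan does not say that missed doses are made up. The Protocol Summary gives 12 months for treatment, and 13 × 28 = 364 days. If three doses are lost, the figures become 8, 4 and 0.

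**Discontinuation proportion.** Section 14.7 summarises safety data as numbers and proportions. With the planned arm sizes in 14.6, one patient is 1/43 = 2.3 points (combination) or 1/18 = 5.6 points (reference).

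**Number of patients.** The documents give no rate for these events. As an assumption only, combined rates of 1%, 2% and 5% among 61 treated patients give 61 × 0.01 = 0.6, 61 × 0.02 = 1.2 and 61 × 0.05 = 3.1 patients.

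**Primary analysis set.** For an event after dose 1 or 2, 6.2.1 means discontinuation before C3D1, so a Stage 1 patient is replaced. Under 6.3 the patient is on hold, is not replaced, and is evaluable if blood is drawn at C3D1. Stage 2 patients are not replaced under either rule.

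**Safety counts.** The event itself is a Grade 3 or greater AE whether or not dosing restarts. The Bayesian rule in 14.7.1 counts patients with such an event, so an affected patient is already counted.

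**The case against.** The best defence is that 6.2.1 is phrased as a requirement and 6.3 as guidelines, so 6.2.1 plainly controls. That is probably the intention, but no sentence says it. Nor can 6.3 be read as covering holds only. It orders permanent discontinuation for Grade 3–4 pulmonary events, infusion reactions and neuropathy and for Grade 4 hypophysitis, in line with 6.2.1. A site would therefore take the resume rows as deliberate.

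A second defence is that the 6.3.3 row also serves diarrhea that is not treatment-related, since 6.3.3 asks for other causes to be evaluated. That is fair, but it leaves the contradiction for related events. Section 6.2 says immune-mediated events should generally be attributed to both drugs, so that case will be common among events managed under these rows.

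A third defence stands in part. The 7-day rule is generic, while the myositis and pancreatitis rows are event-specific, so those rows could be read as refinements. The documents do not settle this, which is why these conflicts are ranked below the first two.

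The safeguards also stand. The diarrhea/colitis, adrenal, myositis, pancreatitis and hypophysitis rows all direct corticosteroids, so the taper of at least 1 month applies before any restart. The amylase/lipase row only asks that steroids be considered. The Grade 3 myositis row also requires contact with the PI, and 6.2.1 stops treatment for any event that the investigator judges a substantial risk.

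**Conclusion.** The contradiction is real and should be fixed. It is unconditional for treatment-related Grade 3 diarrhea/colitis and for Grade 3–4 adrenal insufficiency, and conditional on duration for the other rows in the table.

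Three stronger conclusions are tempting, and the documents do not support them:

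- A reader might infer that patients are dosed through severe toxicity. Both sections stop dosing at onset; the dispute is about re-exposure after recovery to Grade 1 or better, normally after a steroid taper.
- A reader might infer that 13 − k doses are actually at stake. That is a ceiling, and the hold and taper reduce it.
- A reader might infer that the efficacy decision or the safety stopping boundaries are compromised. The Grade 3 or greater AE count and the Bayesian rule are untouched. The only route to the primary analysis is Stage 1 replacement for events before C3D1, which is minor but not nil.

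The effect is 2.3 or 5.6 points on the discontinuation proportion per affected patient, with planned arm sizes as denominators. How many patients that means is unknown; the 0.6 to 3.1 above rests wholly on assumed rates.

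**What to change.** Make these wording changes by amendment:

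1. At the start of 6.3, state that the 6.2.1 discontinuation criteria govern wherever the two sections differ.
2. State whether the re-challenge footnotes apply to events that meet 6.2.1. They are footnote c in most tables, a for infusion reactions and e for cytokine-release syndrome. Left open, they bring the conflict back.
3. In 6.3.3, change the Grade 3 row to permanent discontinuation for treatment-related events.
4. In 6.3.4, split the adrenal row into Grade 2 (hold and resume) and Grade 3–4 (discontinue), and keep the work-up hospitalisation note.
5. Check the remaining 6.3 rows against 6.2.1, including myositis, pancreatitis, amylase/lipase and hypophysitis. For each, either apply the 6.2.1 duration limit or write an explicit exception into 6.2.1. Which of the two is a clinical choice that the documents leave open.

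This adds no patients, visits or tests. The cost is possibly a few more discontinuations, at most one per affected patient and already required by 6.2.1 as written. Each gives up at most 13 − k doses, and fewer in practice.

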6.3.3 Gastrointestinal Disorders or Events

Immune-mediated gastrointestinal events are a potential risk with tiragolumab.

Management guidelines for diarrhea or colitis are provided in the table below.

All events of diarrhea or colitis should be thoroughly evaluated for other more common etiologies. For events of significant duration or magnitude or associated with signs of systemic inflammation or acute-phase reactants (e.g., increased C-reactive protein, platelet count, or bandemia): Perform sigmoidoscopy (or colonoscopy, if appropriate) with colonic biopsy, with three to five specimens for

standard paraffin block to check for inflammation and lymphocytic infiltrates to confirm colitis diagnosis.

Management Guidelines for Gastrointestinal Disorders or Events (Diarrhea or Colitis)

| Event | Management |
|------------------------------|---|
| Diarrhea or colitis, Grade 1 | 
 ● Continue atezolizumab and tiragolumab. ● Initiate symptomatic treatment. ● Endoscopy is recommended if symptoms persist for > 7 days. ● Monitor closely. |
| Diarrhea or colitis, Grade 2 | 
 ● Withhold atezolizumab and tiragolumab for up to 12 weeks after event onset.^a ● Initiate symptomatic treatment. ● If strong clinical suspicion for immune-mediated colitis, start empiric IV steroids while waiting for definitive diagnosis. ● Patient referral to GI specialist is recommended. ● For recurrent events or events that persist > 5 days, initiate treatment with corticosteroids equivalent to 1–2 mg/kg/day oral prednisone. If the event does not improve within 48 hours after initiating corticosteroids, consider adding an immunosuppressive agent. ● If event resolves to Grade 1 or better, resume atezolizumab and tiragolumab.^b ● If event does not resolve to Grade 1 or better while withholding atezolizumab and tiragolumab, permanently discontinue atezolizumab and tiragolumab and contact Medical Monitor.^c |

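### Section 6.2.1 ends treatment for Grade 3 treatment-related diarrhea/colitis and Grade 3 or higher adrenal insufficiency, Sections 6.3.3 and 6.3.4 resume it on resolution, and nothing says which governs

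*Combined protocol and SAP*

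**What the plan says.** **Section 6.2.1 (discontinuation criteria).** For diarrhea and colitis: "Grade 3 treatment-related uveitis, pneumonitis, bronchospasm, diarrhea, colitis, neurologic toxicity, hypersensitivity reaction, or infusion reaction of any duration requires discontinuation". For adrenal insufficiency: "For Grade ≥ 3 adrenal insufficiency or Grade ≥ 4 hypophysitis, treatment needs to be discontinued regardless of control with hormone replacement". The only relief attached to the adrenal rule is a note on hospital admission for diagnostic workup without severe symptoms. The Grade 3 endocrine exemption leaves the condition out: "Grade 3 treatment-related endocrinopathies (excluding adrenal insufficiency and hypophysitis) adequately controlled with only physiologic hormone replacement do not require discontinuation". The Grade 4 endocrine exception leaves it out as well.

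**Section 6.3.3, Grade 3 diarrhea or colitis.** Both drugs are held for up to 12 weeks from onset, and then: "If event resolves to Grade 1 or better, resume atezolizumab and tiragolumab". Permanent discontinuation applies only if the event fails to resolve. The section also asks sites to look for other causes: "All events of diarrhea or colitis should be thoroughly evaluated for other more common etiologies".

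**Section 6.3.4, adrenal insufficiency Grade 2–4 (a single row).** Both drugs are held for up to 12 weeks, and then: "If event resolves to Grade 1 or better and patient is stable on replacement therapy, resume atezolizumab and tiragolumab".

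**Places where a precedence rule might sit.** Section 6.0 lets the PI make further holds and modifications beyond those listed. Section 6.2 permits temporary suspension in general terms. Section 5.6 lists reasons for stopping. Section 6.3 does not refer back to 6.2.1. None of them ranks 6.2.1 against the 6.3 tables.

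**The concern.** The same treatment-related event at the same grade gets two default instructions. For adrenal insufficiency the clash is direct: control on replacement, which 6.2.1 treats as irrelevant, is a condition that 6.3.4 uses to restart.

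The main stake is safety. These are resected stage II patients, and Section 1.1 justifies ctDNA selection partly by the wish to spare patients needless toxicity. Whether someone is re-exposed after Grade 3 colitis or Grade 3–4 adrenal insufficiency should not turn on which table a site consults. Both conditions are on the adverse-event-of-special-interest list in 7.1.3.1, so they are anticipated. Expedited reporting brings the event to attention but does not tell the site which rule to apply.

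The second stake is the data. Section 2.0 counts discontinuations due to treatment-related AEs in the safety endpoint, and Section 5.3 ties replacement of Stage 1 patients to discontinuation before C3D1.

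**Working it through.** The plan states no figure to reproduce, so the check is textual.

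**1. The two pairs of instructions**

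| Event | 6.2.1 | 6.3 table |
|---|---|---|
| Grade 3 treatment-related diarrhea/colitis | Discontinue, whatever the duration | Hold up to 12 weeks; resume at Grade 1 or better (6.3.3) |
| Grade 3–4 adrenal insufficiency | Discontinue, even if controlled on replacement | Hold up to 12 weeks; resume at Grade 1 or better and stable on replacement (6.3.4) |

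For a resolving event, no single action satisfies both columns.

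**2. Can the sections be reconciled?**

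- *Attribution.* Section 6.2.1 covers treatment-related events only, so a hold while other causes are excluded fits both sections. The conflict begins once the event is attributed to study drug. The 6.3 tables are for drug-specific events, so the sections do overlap.
- *Discontinuation read as a hold.* Section 6.2 treats dose interruption and treatment discontinuation as separate things.
- *Footnote c (re-challenge).* It is attached to the permanent-discontinuation bullets. The resume bullets carry footnote b, on steroid taper. Resumption is therefore the ordinary path in these rows, not an exception to stopping.
- *The admission note.* It does not reach a Grade 3–4 event that is controlled on replacement.
- *Built-in discretion.* Where 6.2.1 wants flexibility it says so, for Grade 3 AST/ALT and for certain Grade 4 endocrine events, each with Medical Monitor involvement. Neither disputed event has such a clause.

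**3. Is a difference intended?** For other events in the same 6.2.1 list the tables agree with it: Grade 3 pulmonary (6.3.1), eye (6.3.6), infusion-reaction (6.3.8) and neuropathy (6.3.12) rows all stop permanently. Grade 3 diarrhea/colitis stands out, and no reason is given.

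**4. Which analyses depend on the choice?**

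- *Discontinuation count (2.0).* Each affected patient changes it by at most one. Planned numbers are 36 + 25 = 61 treated, 18 + 25 = 43 on the combination and 18 on the reference arm. One patient is thus 1/61 = 1.6, 1/43 = 2.3 or 1/18 = 5.6 percentage points. This gives scale only. Simple randomization does not guarantee 18 per arm, and replacements would enlarge the denominators.
- *Primary endpoint.* Evaluability requires the C3D1 draw (5.3). With 28-day cycles and no delays, C3D1 falls 2 × 28 = 56 days after C1D1. For an event in that window, a Stage 1 patient who is stopped is replaced and one who is held is not. The choice can therefore change who is among the 18 combination patients judged against the threshold of 3 clearances (14.5). Stage 2 patients who stop before C3D1 are not replaced.
- *Grade 3 or greater AE count (14.3) and Bayesian toxicity rule (14.7.1).* Both count the event whether drug is held or stopped.

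**5. Neighbouring rows.** Section 6.2.1 also has a general stop: "Any Grade ≥ 3 non-skin, treatment-related AE lasting > 7 days or recurs", with listed exceptions. The Grade 3 myositis (6.3.15) and pancreatitis (6.3.10) rows resume on resolution without the 7-day limit, although they do stop recurrent events. Grade 3 hypophysitis (6.3.4) follows the same pattern, but 6.2.1 itself is less clear there: it names hypophysitis at Grade 4 yet excludes it from the Grade 3 exemption. Section 6.3.7 only withholds for myocarditis and pericardial events up to Grade 4, while 6.2.1 stops any Grade 4 treatment-related AE outside its exceptions, and cardiac events are not among those.

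**The case against.** The strongest reply is that a sensible default exists. Section 6.2.1 is titled as discontinuation criteria and uses mandatory verbs, whereas 6.3 offers management guidelines. On that reading an investigator who stops breaches nothing, and the live risk runs one way, toward wrongful resumption. The gap is also narrower than stop-for-ever against resume, because footnote c in 6.3 allows documented re-challenge after full recovery even from permanent discontinuation. These points make re-exposure the main risk and temper its size. They do not supply a precedence rule, and a site that follows the 6.3 row is following the protocol as written.

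A second reply is that a reader might infer more than the documents support. Four such readings should be set aside:

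- *Any hold for Grade 3 diarrhea breaches 6.2.1.* It does not while attribution is pending.
- *The discontinuation count is the only endpoint touched.* Section 5.3 shows otherwise for events before C3D1.
- *The primary result or safety monitoring is compromised.* No rate is given for either event, so no direction or size of effect on clearance can be claimed, and the toxicity rule counts the event either way.
- *Section 6.2.1 should simply override 6.3.* Section 6.3 stops some events that 6.2.1 does not list at low grades: Stevens-Johnson syndrome or toxic epidermal necrolysis, myasthenia gravis and Guillain-Barré syndrome at any grade, Grade 2 myelitis, and meningoencephalitis at all grades. Silence in 6.2.1 is not strictly a conflict, but a stricter-instruction rule keeps those stops beyond doubt.

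**Conclusion.** The inconsistency holds for two events: treatment-related Grade 3 diarrhea/colitis, and adrenal insufficiency of Grade 3 or higher. It should be fixed, mainly to prevent re-exposure to study drug after a toxicity that 6.2.1 says ends treatment. In the reference arm that means atezolizumab alone.

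The effects on the discontinuation count and on the Stage 1 primary-endpoint set are possible and cannot be quantified from the documents. The per-patient percentages are arithmetic ceilings, not expected effects. The conclusion assumes that the event has been judged treatment-related and has resolved as the 6.3 row requires. It does not call the two-stage design or the toxicity boundaries into question. The neighbouring rows belong in the same reconciliation; Grade 3 hypophysitis is arguable rather than a definite conflict.

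**What to change.** 1. Amend the Grade 3 diarrhea/colitis row of 6.3.3 and split the adrenal insufficiency row of 6.3.4 into Grade 2 and Grade 3–4, so that both match 6.2.1. If the sponsor's clinicians intend hold-and-resume, amend 6.2.1 instead.
2. Add a permanent sentence to 6.0: where 6.2.1 and 6.3 differ, the stricter instruction for that event and grade applies unless the row states otherwise. An interim memo alone would leave the neighbouring rows unresolved once it lapsed.
3. In the same amendment, reconcile with 6.2.1 the rows for Grade 3 hypophysitis, myositis and pancreatitis lasting more than 7 days, and for Grade 4 myocarditis and pericardial events.

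The cost is a wording amendment with IRB review and notice to sites. It needs no added procedures and does not change the planned sample size. Under the stricter rule a few patients may lose doses they could have resumed.
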